5.0 Study Procedures

5.1 Study Design

- Describe experimental design of the study. Include sequential and/or parallel phases of the study, including durations, and delineate which interventions are standard of care and which are research.
- Include a description of how anticipated risk will be minimized and include an analysis of risk vs. potential benefit.

- Provide description of the study population (delineate all categories of subjects – patients, providers, family members, employees, etc.). Include anticipated enrollment numbers
- Include rationale for including or excluding certain populations – in particular vulnerable populations.
- As applicable, provide information on any added protections for vulnerable populations.
- If applicable include information on data and/or specimen banking to include where the bank is located, who will own the data and/or specimens, and who is overseeing the repository.

The proposed 4-year, multisite, randomized pragmatic trial will assess the real-world application of bCBT for Veterans with anxiety, as delivered by frontline VA PCMHI providers at three facilities (Houston, San Antonio, and New Orleans). Veteran participants will be randomized to bCBT or to Enhanced Usual Care (EUC). EUC participants will receive anxiety education materials, a note in their medical record indicating the presence of elevated anxiety symptoms, and 4 brief monthly check-in calls with project staff. Participants randomized to bCBT will have the option to receive bCBT for anxiety delivered either in person, via VVC-H, or both. The primary outcome, anxiety symptoms, will be evaluated at 4-, 8- and 12-month follow-ups.

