5.5 Study Evaluations

- Describe all evaluations to be conducted (including screening; tests/questionnaires that will be administered; any procedures that

subjects will be required to complete) and data collection methods. Include materials as an appendix or separate attachment.

Aims 1 & 2 Quantitative Measures: Measures were selected for their strong psychometric properties, ability to detect patient-centered change, and feasibility for adoption/implementation within VA PCMHI clinics.

Anxiety: We chose the Generalized Anxiety Disorder Screener (GAD-7¹⁴) as our primary anxiety measure because of its brevity, psychometrics and, most importantly, because it has been adopted by VHA's national PCMHI program. The GAD-7 is a seven-item self-report instrument that is psychometrically strong and valid for use in the primary care setting^{5,14}. A GAD-7 score of 10 or higher will be required for study inclusion. Treatment response will be defined as a 50% reduction in baseline GAD-7 scores. Note: Study staff will administer the GAD-7 as part of all outcome assessments; bCBT providers will also administer it as part of their MBC practices when delivering bCBT.

The Overall Anxiety Severity and Impairment Scale (OASIS¹⁵) will be a secondary measure of anxiety. Unlike the GAD-7, which will be administered by both research staff and PCMHI providers, the OASIS will only be administered by research staff, thereby avoiding response bias that may occur in the clinical setting. The OASIS is a widely used five-item measure of anxiety for primary care settings^{5,16} assessing anxiety frequency, anxiety severity, avoidance behaviors, social interference, and interference at work, school, or home¹⁵. The OASIS has demonstrated good internal consistency, and convergent and divergent discriminative validity in primary care^{16,17}. A 50% reduction in symptoms on the OASIS is indicative of treatment response^{5,6}.

Quality of Life and Functional Status: We will assess quality of life using the 12-item Short Form Health Survey for Veterans (SF-12V¹⁸), an instrument adopted by VHA as a measure of functional status. SF-12V responses can be summarized in component scores for physical (PCS) and mental (MCS) functioning. Minimally clinically important differences (MCIDs) for PCS and MCS scores are a change of 5.0 or more^{19,20}.

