Analyses will use data from the mixed-method formative evaluation described above. Qualitative pre-implementation data will be analyzed using rapid qualitative analysis, a systematic and rigorous process, to provide data in real-time to tailor the intervention, and identify contextual barriers prior to rollout^{38,39,40}. Implementation and post-implementation interviews with providers and Veterans will be analyzed using directed content analysis⁴¹ consisting of deductive (a priori) codes from the RE-AIM QuEST framework. Inductive (a posteriori) codes that emerge from providers' and Veterans' experiences with the intervention and VVC-H delivery will also be identified. We will utilize Atlas.ti software to facilitate analysis and management of qualitative data. Quantitative data will be collected and analyzed as descriptive data.

Sample Size and Power Calculations

Primary Aim: To determine whether anxiety symptoms (GAD-7) and quality of life (SF-12) differ as a function of the intervention (bCBT for anxiety vs. EUC) at 4-, 8-, and 12-month follow-ups. A three-step sample-size calculation indicates that 225 anxiety patients will need to be randomized to draw conclusions regarding the primary hypothesis that bCBT will be superior to EUC at 4-, 8, and 12-month assessments.

Step 1: Power to detect GAD-7 differences. A sample size of 138 anxiety patients is needed to detect an effect size = 0.38 for the differences between bCBT and EUC GAD-7 outcomes using a two-sided t-test with 80% power at the .05 significance level, adjusted for repeated measures³⁷. The formula for the sample size, adjusting for repeated measures, is

$$N = \frac{2 * (Z_{(1-\alpha/2)} + Z_{(1-\beta)})^2 [1 + (T - 1) \rho]}{d^2 T}, \text{ where } N \text{ is the sample size per group, } Z_{(1-\alpha/2)} \text{ and}$$

$Z_{(1-\beta)}$ are the $(1-\alpha/2)$ and $(1-\beta)$ percentiles of the normal distribution, T is the number of follow-up measures, ρ is the correlation coefficient of the repeated measurements, and d is the effect size⁴². Solving this with $T = \text{three follow-up measurements after baseline}$, $d = 0.38$, and $\rho = .7$ yields a sample size per group of 69, and total sample $N^t = 138$.

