Quality of Life Outcomes. Our prior study of patients with anxiety or depression¹⁰ resulted in mean, standard deviations, and effect size of 7, 11, and 0.3 respectively for the SF12V mental component score (MCS). SAS[®] proc power indicated that a two-sided t-test with 80% power at the .05 significance level requires a sample of 40 patients per group (80 total). Because the sample required for the anxiety measure (GAD-7; $n=138$) is greater than that needed for the

quality-of-life measure (SF12V; n=80), adjusting for repeated measures, unequal sample, and clustering on provider is presented below for the anxiety measure.

Step 2: Unequal Randomization. To increase power for the project's secondary and implementation outcomes and to reduce unnecessary recruitment, unequal allocation will be used where approximately 60% of Veterans will be randomized to bCBT. As noted by Dumville et al.³⁷, an unequal number of participants per group is an under-used technique that offers advantages for randomized trials, most notably, reduction in unnecessary recruitment. Revised total sample size $N' = N(1+k)^2/4k$, where $N=138$ and $k=1.5$, which gives revised total sample $N'=145$. The individual sample size in each of the two groups are $N'/(1+k)$ and $kN'/(1+k)$; giving $n=58$ in the EUC group and $n=87$ in the bCBT group.

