## DATA ANALYSIS PLAN

### Primary aim: Anxiety and Quality of Life differ as a function of bCBT for anxiety vs. EUC

All analyses will be done on an intention-to-treat basis, and participants will be analyzed in the group to which they were randomized. We will first determine whether participants randomized to the two study arms differed on baseline characteristics, age, race, gender, medical or mental health comorbidities, and anxiety. Chi-square tests will be used for categorical variables and t-test for continuous and ordinal variables.

We will examine the normality of the distributions of both primary outcomes and will consider transformations such as the log or the inverse. Because we are using an unequal randomization (see sample size section), it is especially important to test the assumption about the homogeneity of the variance of the residuals across the levels of the independent variables. For analyses of our primary outcomes, we will test the homogeneity assumption before testing for differences between the bCBT and EUC groups. If the assumption of equal variances is violated, we will use statistical tests such as the approximate t-test, which uses individual sample variances instead of the pooled variance. In addition, we will obtain Satterthwaite's approximation of the degrees of freedom. For the regression models, we will test whether the residual variances are equal and, if necessary, we will fit unequal variance models to obtain better estimates of the standard errors of the difference between groups. We will calculate the absolute differences in outcome measures between baseline and 12-month follow-up and the effect sizes of the bCBT group compared with EUC. We will also examine effect sizes for the bCBT group baseline vs. post-treatment and 8-month follow-up.

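### The SF-12 sample size of 40 per group follows from 7/11 = 0.636, not from the effect size of 0.3 cited beside it; if 0.3 is the between-arm effect, this outcome has about 51% power and sets the sample size.

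*Protocol*

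**What the plan says.** The Quality of Life paragraph in Protocol 5.6 reports that a prior study "resulted in mean, standard deviations, and effect size of 7, 11, and 0.3 respectively for the SF12V mental component score (MCS". It then states that "a two-sided t-test with 80% power at the .05 significance level requires a sample of 40 patients per group (80 total". It does not say which of the three figures went into the calculation, or whether the mean of 7 is a difference between arms or a change within one group.

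The paragraph uses the result to set quality of life aside. It reads "Because the sample required for the anxiety measure (GAD-7; $n=138$) is greater than that needed for the" quality-of-life measure (80), and from there only the GAD-7 goes through the steps for unequal allocation, provider clustering and attrition that lead to 225. The GAD-7 number is the sample "needed to detect an effect size = 0.38 for the differences between bCBT and EUC GAD-7 outcomes", with an adjustment for three repeated measurements.

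The status of the SF-12 differs between sections. Protocol 3.0 puts it in the primary hypothesis and primary aim together with the GAD-7. The power section of 5.6 restates that aim, and the SAP says "We will examine the normality of the distributions of both primary outcomes". Protocol 5.1 names one outcome only: "The primary outcome, anxiety symptoms, will be evaluated at 4-, 8- and 12-month follow-ups".

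**The concern.** A mean of 7 with a standard deviation of 11 is a standardized effect of 0.636, about twice the 0.3 given in the same sentence. A reader who takes 0.3 as the expected effect will see that 40 per group is far too few.

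The figure also matters for what follows, because 80 being smaller than 138 is the only reason given for sizing the trial on the GAD-7 alone. If the order is reversed, an outcome named in the primary hypothesis has never been powered. A null SF-12 result would then say little. If both outcomes have to succeed, the power of the joint claim cannot exceed that of the SF-12.

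**Working it through.** **Inputs.** From the Quality of Life paragraph (5.6): 7, 11, 0.3, two-sided .05, 80% power, 40 per group. From Step 1: GAD-7 effect size d = 0.38, T = 3 follow-ups, correlation ρ = .7, 69 per group (138 total). From Steps 2 and 3: 87 bCBT and 58 EUC before inflation, clustering factor 1.25, attrition 25%, 145 + 80 = 225 randomized. No correlation is given for the SF-12, so .7 is borrowed from the GAD-7 and varied below.

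**1. The plan's own figure.** A two-sample t-test at d = 7/11 = 0.636 needs 39.7 per group, so 40. This matches the protocol.

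**2. The same test at d = 0.3.** It needs 175.4, so 176 per group (352 total). At 40 per group its power is 26%. One-sided and one-sample variants at 0.3 do not give 40 either (139 and 69 at the lowest).

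**3. Both outcomes on the Step 1 basis.** The formula is n per group = 2(1.960 + 0.842)²[1 + (T − 1)ρ]/(d²T). With T = 3 and ρ = .7 the bracket divided by T is 2.4/3 = 0.8, so n = 2 × 7.849 × 0.8/d² = 12.558/d².

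| Outcome and effect | n per group | Total |
|---|---|---|
| SF-12, d = 0.3 | 12.558/0.09 = 139.5, so 140 | 280 |
| SF-12, d = 7/11 | 12.558/0.405 = 31.01, so 32 | 64 |
| GAD-7, d = 0.38, formula result | 12.558/0.1444 = 86.97, so 87 | 174 |
| GAD-7, d = 0.38, as stated | 69 | 138 |

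The stated 69 does not follow from the stated two-sided inputs. That is a separate matter, but 140 exceeds both 69 and 87. Because 0.3 is smaller than 0.38, the SF-12 needs more patients under any common formula with the same ρ. At 7/11 it needs fewer. The protocol's own comparison mixes bases, since 138 is adjusted for repeated measures and 80 is not.

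**4. Power with 225 randomized.** Removing attrition and clustering gives 145 × 0.75/1.25 = 87 for bCBT. For EUC the plan's pre-inflation figure is 58 (80 × 0.75 = 60 after its rounding up).

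- One visit: SE = √(1/87 + 1/58) = 0.1695 in SD units.
- Three-visit average: 0.1695 × √0.8 = 0.1516.
- d = 0.3, three-visit average: Φ(0.3/0.1516 − 1.960) = Φ(0.019) = 51% (52% with 60 in EUC).
- d = 0.3, one visit: Φ(0.3/0.1695 − 1.960) = Φ(−0.190) = 42%.
- d = 0.3, three-visit average, other correlations: 58% at ρ = 0.5 and 45% at ρ = 0.9.
- d = 7/11, three-visit average: Φ(0.636/0.1516 − 1.960) = Φ(2.24) = 99%.

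**5. Can the three figures describe one effect?** On the correlation scale, r = d/√(d² + 4) = 0.636/√(0.405 + 4) = 0.30. So yes, if 0.3 is a correlation-type effect size.

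**The case against.** The strongest reply is that 0.3 is undefined. As step 5 shows, 7, 11 and 0.3 fit together if 0.3 is on the correlation scale. Then 40 per group is right and the GAD-7 does set the sample size. The definition lies in the prior study, which is not part of these documents. This stands, and it makes the power loss conditional. Against it, Step 1 uses effect size for a standardized difference d, and nothing tells the reader that the term changes meaning in the next paragraph.

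It is also fair that ρ = .7 belongs to the GAD-7, so 140 per group and 51% should be read with their range.

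Three stronger readings are tempting, and the documents do not support them:

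- A reader might infer that the GAD-7 fails to set the size even at the protocol's minimal important difference, which "for PCS and MCS scores are a change of 5.0 or more". The plain t-test at 5/11 needs 77 per group, 154 in total, which is above 138. But 154 is unadjusted and 138 is adjusted. By the Step 1 formula the need is 12.558/0.2066 = 60.8, so 61 per group or 122 in total, below 138. The 5 points are also described as a change and not as a difference between arms.
- A reader might infer that the false-positive rate for the primary claim is inflated. That holds only if either outcome alone can carry the claim. Protocol 3.0 joins the two outcomes, and if both must succeed there is no inflation. The .05 level appears only in the sample-size text.
- A reader might infer that the statement about 80 patients must be deleted whatever the answer. If 7/11 is the between-arm effect, it is correct.

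**Conclusion.** The paragraph is wrong as written. It cites an effect size of 0.3 and states a sample size that comes from 0.636, and on the scale that Step 1 uses for effect size the two do not agree.

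The consequence depends on what 0.3 is:

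- **A standardized between-arm difference.** The requirement is 280 to 352 patients before the later adjustments, not 80. The SF-12 replaces the GAD-7 as the outcome that sets the size. The planned trial has about 51% power for the three-visit average and 42% at one visit. This assumes the plan's effective sizes of 87 and 58 and, for the average, ρ = .7.
- **The same effect as 7/11 on another scale.** Power is about 99%, the order of the two requirements stands, and only clarification is needed.

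Under either reading, 80 and 138 are on different bases, and the sections disagree on whether the SF-12 is primary.

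**What to change.** 1. In the Quality of Life paragraph of 5.6, state what 0.3 measures, whether 7 is a difference between arms, and which value is the assumed between-arm effect.
2. Put the SF-12 and GAD-7 requirements on the same basis, both with or both without the repeated-measures adjustment.
3. If 0.3 is the between-arm effect, withdraw the statements that 80 patients suffice and that the GAD-7 requirement is the larger. Report SF-12 power at 225 with its assumed correlation and range (about 51%; 45% to 58% for ρ from 0.9 to 0.5). If 7/11 is the effect, keep both statements and explain 0.3.
4. Reconcile Protocol 5.1 with 3.0, 5.6 and the SAP on whether the SF-12 is primary, and state whether both outcomes must succeed or either is enough. One way is to make the GAD-7 the single primary outcome and test the SF-12 mental component score next in a fixed sequence. Requiring success on both is another, with joint power then limited by the SF-12.

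The cost is wording in Protocol 3.0, 5.1 and 5.6 and in the SAP. No more patients need to be enrolled. If the GAD-7 becomes the single primary outcome, the SF-12 loses its primary status.

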Consent to audio record bCBT sessions is also included in the written informed consent document and explained as an optional matter, not required for participation. Participants who decline being audio recorded will have a note placed in the research master record indicating such. Providers will be notified via encrypted email of participants randomized to the direct referral group who declined being audio recorded. Providers will ask bCBT participants who consented to audio recording for their verbal consent prior to audio recording bCBT sessions.

Veteran Qualitative Interview:

A subset of Veteran participants randomized to the treatment group will be invited to complete a one-time qualitative interview focused on their experiences receiving bCBT for anxiety through video-to-home and/or in person (see Appendix 5E, Veteran Qualitative Interview ICF). The study will recruit a total of 28 participants that fall into 3 categories: 1) 4 Veterans with no bCBT engagement (0 sessions), 2) 4 Veterans with little engagement in bCBT (1-3 sessions), and 3) 20 Veterans who fully engaged in treatment (4 or more sessions). The third group will be further stratified to include 10 who opted for and 10 who declined VVC-H.

To determine their interest in completing the interviews, participants will be contacted at the 4-month time period or immediately following their decision to end treatment. Veterans that agree to complete the interview will be sent the written informed consent form by mail or VA-approved transmission source. The potential participant will be contacted within two weeks of the mailout to discuss the document and be given an opportunity to ask questions about the interview. Upon receipt of a valid, signed study informed consent form the participant will be contacted and scheduled for the qualitative interview to occur within 2 weeks.

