To compare changes in anxiety symptoms between the two groups over time, we will use a longitudinal, mixed-model analysis containing terms for the intercept, treatment, time, and interaction between time and treatment. In separate analyses, we will compare changes in quality-of-life between the two groups over time using a similar mixed-model approach. The mixed-model analysis will allow us to nest patients by site. Any baseline characteristics found to be significantly different between bCBT and EUC will be included in the model, as will any differences in mental health service use. The four time points (baseline, 4-, 8-, and 12-month) will allow us to assess the immediate impact of treatment and the longer-term retention, improvement, or decay in outcomes. The treatment effect will measure differences between the intervention and control groups at baseline, and the time effect will measure whether there was an overall change over time in the outcome. The term of most interest will be the interaction between time and treatment, which will indicate whether there is a difference over time between the two groups. The use of the random-coefficient model will allow us to fit a line for each participant using his/her available data, including participants with missing values, and maximize the power to detect differences.

Secondary Analyses: Prediction of bCBT response and VVC-H use:

We will run two logistic regression analyses using only data from participants who received bCBT. In analysis 1, we will identify characteristics that predict response to treatment as defined as a reduction of 50% on the GAD-7. Predictor variables will include: baseline anxiety severity (GAD-7 score), presence of specific anxiety diagnoses (GAD, Panic, Social Anxiety, Other), medical comorbidities, and brief CBT-related factors (number sessions received and treatment engagement). In analysis 2, we will identify characteristics associated with VVC-H use. VVC-H

use will be classified as any (one or more VVC-H sessions) or none. Predictor variables will include: age, distance to VA facility in miles, medical comorbidities, depression and PTSD (presence or absence), and Veteran self-reported comfort receiving in-person VHA care and confidence using video-based services and technology.

Implementation Analyses (Exploratory):

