Step 3: Provider Inflation Factor. The bCBT sample size was then inflated to account for the intraclass correlation due to clustering of patients within providers⁴³. We also will adjust the sample sizes for both the bCBT and EUC groups to account for attrition. Because only participants receiving bCBT are assigned to a provider, we first determined the average number of bCBT patients per provider (87 bCBT patients/25 providers = 3.5 patients per provider). To account for clustering in the bCBT group, the number of bCBT patients is inflated by the factor $[1 + (\bar{m} - 1) c]$, where \bar{m} is the average number of bCBT patients per provider and c is the correlation among patients seen by the same provider. Based on the sample size of 87 bCBT patients and an assumed correlation among patients of .10⁴³, our inflation factor is 1.25 ($87 \times 1.25 = 109$). Finally, to account for attrition, we assumed an attrition rate at 1 year of 25% ($109 \times (1/0.75) = 145$) gives 145 bCBT patients. A similar clustering inflation factor was not used for the EUC group, as no providers are assigned. Attrition rate of 25% was assigned to the EUC group ($58 \times (1/0.75) = 78$), rounded to 80 for randomization. The final number of randomized patients equates to 225 (145 bCBT and 80 EUC).

Secondary Aims:

Prediction of bCBT response and VVC-H use (bCBT group only). To assess predictors of bCBT response and VVC-H use, at least 10 events per variable in the logistic-regression models are needed to have unbiased estimates of the sample variance of the regression coefficients⁴⁴. No sample-size calculations were conducted for secondary aim, but SAS[®] proc power (version 9.4)⁴⁵ indicated a sample of 145 is adequate for 80% power to test odds ratio of 2.5, and conservative estimates for sample size and assumptions necessary to run the analyses suggest the project will be appropriately powered for 10 variables⁴⁶. Secondary analyses will include 8 variables for aim 2A (bCBT response; model #1) and 8 variables for aim 2B (VVC-H prediction; model #2).

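### The 80% power stated for an odds ratio of 2.5 in Aim 2 counts all 145 patients randomised to bCBT and names no predictor type; a present/absent predictor has at most about 78%, and less once losses are counted

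*Protocol*

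**What the plan says.** Protocol section 5.6, Sample Size and Power Calculations, Secondary Aims, states "No sample-size calculations were conducted for secondary aim". It then adds that proc power "indicated a sample of 145 is adequate for 80% power to test odds ratio of 2.5". No event rate, predictor scale, predictor prevalence, alpha or sidedness accompanies the figure.

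The 145 comes from Step 3 of the same section. There the bCBT group is set at 109 after allowing for provider clustering, and then divided by 0.75 for a 25% attrition rate at 1 year.

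The Secondary Analyses paragraph of section 5.6 sets the analysis population: "We will run two logistic regression analyses using only data from participants who received bCBT". Model 1 predicts response (a 50% fall in GAD-7) from baseline GAD-7 score, specific anxiety diagnoses, medical comorbidities, number of sessions and engagement. Model 2 predicts any use of VVC-H from age, distance, medical comorbidities, depression and PTSD as present or absent, and self-rated comfort and confidence. Section 5.5 codes each diagnosis as present or absent.

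The protocol expects some patients never to start treatment. The qualitative sample in section 5.3 includes "4 Veterans with no bCBT engagement (0 sessions").

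**The concern.** The plan adds patients to cover losses, then quotes Aim 2 power on the enlarged number as if there were none. It also gives one power figure for two models that mix present/absent with continuous predictors, although at the same odds ratio these differ greatly in power.

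Section 3.0 names specific anxiety disorders first among the factors that Aim 2A examines, and these enter as present/absent terms. A non-significant diagnosis would be interpreted alongside a stated 80% power for an odds ratio of 2.5. If real power is well below that, the finding says less than it appears to. The figure also bears on the design: Step 2 of the sample-size section justifies the unequal allocation partly by power for the secondary outcomes.

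**Working it through.** **Inputs from the documents.** Odds ratio 2.5, 80% power, N = 145 (section 5.6, Secondary Aims); 25% attrition at 1 year (Step 3).

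**Assumptions.** Two-sided .05 is not stated for Aim 2; it is taken from the primary-aim calculation, "using a two-sided t-test with 80% power at the .05 significance level". The documents give no prevalences or event rates, so a range is shown.

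**1. Where 145 comes from.** 87 × 1.25 = 108.75, taken as 109; 109 / 0.75 = 145.3, taken as 145. Undoing the attrition step: 145 × 0.75 = 108.75, or 109.

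**2. The stated 80%.** It cannot be uniquely reproduced because its inputs are missing. The steps below ask which inputs would support it.

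**3. Present/absent predictor, best case.** With predictor and outcome both split 50/50, an odds ratio of 2.5 means response rates of 1/(1 + √2.5) = 0.387 and 0.613, a difference of 0.225.

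Likelihood-ratio test: λ = 2N[(1 − f)K(p0, p̄) + fK(p1, p̄)], where f is prevalence, p0 and p1 are the response rates without and with the predictor, p̄ is overall response, and K(p, q) = p ln(p/q) + (1 − p) ln((1 − p)/(1 − q)). Power is the chance that a noncentral chi-square (1 df, noncentrality λ) exceeds 3.841.

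- N = 145: λ = 7.41, power 77.7%.
- N = 130: λ = 6.65, power 73%.
- N = 109: λ = 5.57, power 65.6%.

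Other approximations at N = 145:

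- Pooled z: (0.2251 − 1.96 × 0.0830)/0.0809 = 0.77, power 78.0%.
- Unpooled z: 0.2251/0.0809 − 1.96 = 0.82, power 79.5%.
- Wald test of the log odds ratio: 76.7%.

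A grid over prevalence and response from 10% to 90% put the likelihood-ratio maximum at 50/50 for both 145 and 109, so these figures are ceilings.

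**4. Other prevalences, 50% response, likelihood-ratio test.**

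| Prevalence | Power, N = 145 | Power, N = 109 | N for 80% power | Odds ratio at 80% power, N = 145 | Odds ratio at 80% power, N = 109 |
|---|---|---|---|---|---|
| 50% | 77.7% | 66% | 154 | 2.6 | 3.0 |
| 30% | 70% | 58% | 186 | 2.8 | 3.4 |
| 20% | 57% | 46% | 247 | 3.4 | 4.2 |

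**5. Continuous predictor, odds ratio 2.5 per SD.** Power = Φ(√(N·P(1 − P)) × ln 2.5 − 1.96), with P the event rate.

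| Event rate | N = 145 | N = 109 |
|---|---|---|
| 10% | 91% | 82% |
| 20% | 99% | 97% |
| 50% | over 99% | over 99% |

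**6. What is left out.** All these figures are for a single predictor. If the other predictors explained 10% or 20% of the variance of the one tested (assumed), best-case Wald power at 145 would fall from 76.7% to 72% or 67%. Clustering by provider, for which the plan assumes a correlation of .10, is also ignored.

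**The case against.** The strongest reply is that the protocol never claims 80% power for a binary predictor. It names no predictor type, and for a continuous one the statement is comfortably true. A reader might infer that the 80% is an arithmetic error. The documents do not support that, because with its inputs unstated the figure is undefined rather than shown to be wrong. The best-case gap at 145 is also small: 0.5 to about 3 points, depending on the approximation. A one-sided .05 test would reach 86%, though nothing in the documents suggests one-sided testing.

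A reader might also infer that both models drop to 109. They need not. Section 5.5 takes VVC-H use from note templates and chart review, so model 2 loses mainly patients with no session. For model 1, the 25% is a 1-year rate and the time point for response is not given. Treatment lasts up to 4 months, and patients who stop treatment may continue with assessments (section 5.7). An earlier time point falls between the two columns.

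Nor is Aim 2 only about yes/no factors: section 3.0 also asks about number of sessions and engagement. And no passage says that a null diagnosis term will be reported as no effect, so that risk is one of interpretation.

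Two things remain. The single unqualified figure covers the diagnosis terms, and for these no prevalence or event rate brings a two-sided .05 test to 80% at 145. And 145 is the randomised number, not the expected analysis set.

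**Conclusion.** The point holds in limited form. The stated power is unsupported for the present/absent predictors and is quoted at a number that makes no allowance for loss.

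- **Binary predictor, all 145 analysed:** at most about 78%, reached only at 50/50. The shortfall there is slight, but it grows to about 10 points at 30% prevalence and 23 at 20% with 50% response.
- **Model 1 with response at 12 months and 25% loss (N = 109):** at most about 66%. A true odds ratio of 2.5 for a diagnosis present in 20% would be missed about 54% of the time, against 43% if all 145 were analysed.
- **Continuous predictor per SD:** the claim stands, with at least 91% power at 145 and 82% at 109 for event rates of 10% to 50%, before adjustment.

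These results rest on two-sided .05, assumed prevalences and event rates, and single-predictor tests. Adjustment for correlated predictors would lower them, and provider clustering could do so too.

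**What to change.** Replace the sentence in section 5.6, Secondary Aims, with power or the detectable odds ratio at the expected analysed number for each model, separately for binary and continuous predictors. State alpha, event rate, prevalence and, for model 1, the time point at which response is judged.

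Possible wording for model 1, if response is judged at 12 months: with about 109 bCBT patients analysed, 50% response and two-sided .05, the odds ratio detectable with 80% power is about 3.0, 3.4 and 4.2 for a binary predictor present in 50%, 30% and 20% of patients, before adjustment for other predictors or provider clustering. If all 145 were analysed, the values would be about 2.6, 2.8 and 3.4.

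For model 2, start from the number expected to attend at least one session. Any power given for continuous predictors should carry its event rate, since at 109 it falls to 82% when the event rate is 10%.

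Do not claim 80% power at 2.5 for the present/absent predictors. Report their odds ratios with confidence intervals, and state that a non-significant diagnosis term is not evidence of no association.

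The cost is a change of wording and a less favourable stated detectable odds ratio. No extra patients are needed.
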